#### 8.2.15. Subject-Rated Treatment Satisfaction at 24 Hours Postdose - PPMQ-R

The PPMQ-R consists of 29 questions that assess a subject’s satisfaction with migraine medication in terms of the following subscales: efficacy (11 questions), function (4 questions), ease of use (2 questions) and cost (2 questions), as well as the degree to which side effects were tolerated (tolerability; 10 questions).

In addition, three global items measuring subject satisfaction in terms of medication effectiveness, side effects and overall satisfaction are included. Items that evaluate treatment satisfaction are scored on a seven-point Likert-type scale from 1 (very satisfied) to 7 (very dissatisfied); whereas items that evaluate tolerability of side effects (i.e. bothersomeness of side effects) are scored on a five-point Likert-type scale from 1 (not at all) to 5 (extremely). For this study, the two items that comprise the cost subscale will not be used since subjects will not pay for the study drug; therefore, 27 questions and three global items will be used.

Each subscale score and the total score will be transformed to range from 0 to 100 with higher scores indicating better satisfaction or tolerability. Subscale scores and Total scores (except the Total Raw core) are transformed to a 0 to 100 range by subtracting the lowest possible scale score, dividing by the range of the scale and multiplying by 100. The individual three Global items will not be transformed. The total score consists of the average of the efficacy, function, and ease of use subscale scores. If a response is missing, the particular subscale or global item will be considered non-evaluable. If a subscale or global item is deemed non-evaluable, or missing, the corresponding total score will also be considered non-evaluable and assigned as missing.

The scores at 24 hours postdose for each subscale score, each global item score, the total score, and the total raw score will be summarized by treatment group for the FAS1 and FAS2. The corresponding p-values from the Wilcoxon rank-sum test will be computed for the comparison between treatment groups.

The change from baseline to 24 hours for each subscale score, each global item score, the total score, and the total raw score will also be analyzed using the Wilcoxon signed-rank test. Baseline scores for each subscale score, each global item score, the total score, and the total raw score will be summarized by treatment group, and will be

compared to 24 hours postdose scores for the DFN-15 group only. The corresponding p-value from the Wilcoxon rank-sum test will be computed for these comparisons.

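### SAP 8.2.15 gives a PPMQ-R 0–100 formula with no reversal step, so as printed the best response scores 0 and the worst 100, against the stated direction

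*SAP*

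**What the plan says.** PPMQ-R treatment satisfaction at 24 hours is a secondary endpoint in each double-blind period (protocol 10.4.2; SAP 4.2). SAP 8.2.15 sets out the scoring:

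- **Item coding.** Satisfaction items use a "seven-point Likert-type scale from 1 (very satisfied) to 7 (very dissatisfied"). Tolerability items, which ask how bothersome side effects were, use a "five-point Likert-type scale from 1 (not at all) to 5 (extremely").
- **Intended direction.** Subscale and total scores are put on 0 to 100 "with higher scores indicating better satisfaction or tolerability".
- **Formula.** This is done "by subtracting the lowest possible scale score, dividing by the range of the scale and multiplying by 100".
- **Total.** "The total score consists of the average of the efficacy, function, and ease of use subscale scores".
- **Global items.** "The individual three Global items will not be transformed".
- **Total raw score.** It is exempt from the transformation and is reported, but it is not defined.

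The 24-hour scores are summarised by group and compared with the Wilcoxon rank-sum test. For change from baseline, "each subscale score, each global item score, the total score, and the total raw score will also be analyzed using the Wilcoxon signed-rank test".

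**The concern.** The item coding, the stated direction and the formula cannot all hold. On both item scales a lower number is the better answer. Subtracting the minimum and dividing by the range is an increasing function, so a lower number stays lower after transformation. The result is a 0–100 score on which higher means worse, while the text says higher means better.

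The coding does not look like a typing slip. SAP 8.2.14 lists the same 7-point order for the 2- and 4-hour satisfaction question and forms its satisfied category from scores 1 to 3. No reverse-coding step appears in 8.2.15, in the SAP's list of changes from the protocol (section 11), elsewhere in the SAP, or in the protocol.

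What is at stake is how the endpoint is read. A two-sided p-value does not show which arm did better; the reader takes that from the group summaries and the changes from baseline. Those are what would flip if the formula were programmed literally, so a benefit read under the stated direction would look like harm, and harm like benefit.

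**Working it through.** **Inputs, all from SAP 8.2.15.** Efficacy has 11 items, function 4 and ease of use 2, each coded 1–7. Tolerability has 10 items coded 1–5. The two cost items are dropped: 11 + 4 + 2 + 10 = 27, which matches the SAP's count of questions used.

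**Printed formula:** T = (S − min)/(max − min) × 100, where S is the sum of the items. Using item means gives the same T.

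**Reversed formula:** R = (max − S)/(max − min) × 100.

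| Subscale | Best sum | Worst sum | Range | T best / worst | R best / worst |
|---|---|---|---|---|---|
| Efficacy | 11 | 77 | 66 | 0 / 100 | 100 / 0 |
| Function | 4 | 28 | 24 | 0 / 100 | 100 / 0 |
| Ease of use | 2 | 14 | 12 | 0 / 100 | 100 / 0 |
| Tolerability | 10 | 50 | 40 | 0 / 100 | 100 / 0 |

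The total averages the first three rows, so it is also 0 / 100 as printed and 100 / 0 reversed. The plan's 0-to-100 range is reproduced; its stated direction is not.

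**Worked examples.** The item means below are chosen only to illustrate; they are not in the documents and are not estimates for this trial.

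- 7-point scale, group means 3 (better) and 4. As printed: (3 − 1)/6 × 100 = 33.3 and (4 − 1)/6 × 100 = 50.0, so the better group is 16.7 points lower. Reversed: (7 − 3)/6 × 100 = 66.7 and (7 − 4)/6 × 100 = 50.0, so it is 16.7 points higher.
- 5-point scale, group means 2 (better) and 3. As printed: (2 − 1)/4 × 100 = 25.0 and (3 − 1)/4 × 100 = 50.0. Reversed: (5 − 2)/4 × 100 = 75.0 and (5 − 3)/4 × 100 = 50.0. The difference is 25 points the wrong way instead of 25 the right way.

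**Effect on the tests.** T + R = 100 at every possible sum, so the two scorings are mirror images. Group differences and changes from baseline change sign but not size. Two-sided rank-sum and signed-rank p-values are identical; SAP 6.1.1 makes testing two-sided. In one simulated data set with 200 per group, p was 0.0145 under both scorings and the mean difference went from +6.69 to −6.69.

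**Scope.** Nine scores are reported: 4 subscales, 1 total, 3 global items and 1 total raw score. The formula applies to 4 + 1 = 5 of them, in two double-blind periods.

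**The case against.** The strongest reply is that the intended direction is not in doubt. The SAP states it just before the formula, and the formula can be read as a generic rescaling of a scale score whose items were reverse-coded beforehand. Two outside papers are cited in the same paragraph and were not available here; either may contain the reversal. On that reading the gap is an unstated convention, and a competent programmer would fill it. A slip might also be noticed: the subscales would move against the untransformed global items and the 2- and 4-hour satisfaction scores, and SAP section 14 requires review of all outputs for consistency. No success rule depends on the sign of this endpoint.

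Much of this stands. It makes the harm conditional and limits its weight. It does not remove the conflict, because the SAP prints a coding and a formula and applying one to the other gives the wrong direction. The citation on the formula sentence is, by its title, to a heart-failure questionnaire paper; the PPMQ-R validation paper is cited only on the sentence defining the total. The unseen sources therefore cannot be relied on to settle it. The independent programming and electronic comparison in section 14 test whether two programs agree, and two programs that follow the same printed formula will agree on the same reversed scores.

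A second objection is that swapping in a reversed formula would reverse twice if items had already been recoded. The SAP states no such recoding, but the corrected text should rule it out.

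**Conclusion.** The concern holds. As written, SAP 8.2.15 gives scores that run opposite to their stated direction for four subscales and the total of a listed secondary endpoint, in both double-blind periods. This is a stated rule that gives the wrong answer, not merely missing detail, and it should be fixed.

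The contradiction in the text is certain. Whether outputs would actually come out reversed is not: that assumes the formula is programmed literally on the printed coding and that output review does not catch it. The three global items are unaffected. Two-sided Wilcoxon p-values, the co-primary analyses and the sample size do not change.

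**What to change.** In SAP 8.2.15:

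1. Replace the formula with (highest possible score − observed score)/range × 100 for the four subscales. State that it is applied to items as coded in that section, with no recoding beforehand.
2. Define the total as the average of the transformed efficacy, function and ease of use scores.
3. Keep the three global items on 1 = best, as already planned. SAP 8.2.14 compares the 2- and 4-hour satisfaction score with the same baseline PPMQ-R question, so that question must stay in the same direction. If it were recoded, an unchanged answer of 2 would be compared as 8 − 2 = 6 against 2, a false difference of 4 points.
4. Define the total raw score, and label the direction of every reported PPMQ-R score in the outputs. The table shells were not available, so any existing labels cannot be judged.

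A minor clarification can go in at the same time. The missing-data rule says "If a subscale or global item is deemed non-evaluable, or missing, the corresponding total score will also be considered non-evaluable and assigned as missing". Neither tolerability nor the global items enter the total, so the SAP should say whether a missing value there is really meant to void it.

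The cost is one formula, a few sentences, output labels and a programming check. It needs no new data and adds no patient burden.

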### 8.3. EXPLORATORY ANALYSES

Exploratory analysis will be conducted for the proportion of subjects who are pain-free 2 hours postdose compared between DFN-15 and placebo in the DB1 treatment period with different predose pain grades (Moderate [Grade 2] or Severe [Grade 3]), respectively. The proportion of subjects who are pain-free at 15, 30, and 45 minutes and 1, 1.5, 2 (DB2 period), 4, and 24 hours postdose will also be compared between DFN-15 and placebo: during DB1 treatment period, predose severity = Moderate or Severe; during DB2 treatment period, predose severity = Mild, Moderate or Severe. The corresponding p-values from Fisher's exact test will be computed for the comparison between treatment groups.

Exploratory analysis will also be conducted for the proportion of subjects with their predose MBS among nausea, photophobia and phonophobia absent at 15, 30, and 45 minutes and 1, 1.5, 2, 4, and 24 hours postdose during each DB treatment period. The corresponding p-values from Fisher's exact test will be computed for the comparison between treatment groups for the FAS1 and FAS2. A subject's predose MBS is obtained from eDiary.

### 8.4. SUBGROUP ANALYSES

Exploratory subgroup analyses on the co-primary endpoints will be conducted using the following baseline categories for the FAS1:

- Age (18-34 years, 35-49 years, 50-64 and >=65 years)
- Gender (male and female)
- Ethnicity (Hispanic and non-Hispanic)

For each subgroup, the odds ratio for response and the 95% CI for the odds ratio for each of the co-primary endpoints will be calculated using the treatment group, the subgroup variable, and the treatment-by-subgroup interaction term as covariates in the logistic regression model. Since the results of these subgroup analyses are exploratory, future studies can examine the treatment effect among the subgroup covariates that have a significant treatment-by-subgroup interaction term.

## 9. SAFETY

The SS, SS1, SS2, FAS1, and FAS2 will be used for safety analyses. Safety will be assessed on the basis of AE reports, clinical laboratory data, ECG parameters, physical examinations, extent of exposure and compliance with study drug use, rescue medication use, concomitant medication use, and vital signs.

### 9.1. EXTENT OF EXPOSURE AND COMPLIANCE WITH STUDY DRUG

In this trial, subjects are considered compliant if they treat a migraine attack with study drug. Study drug exposure will be summarized by treatment group and overall for the SS, SS1, and SS2. By definition of the SS1 and SS2, each subject in those cohorts is considered compliant.

During the DB1 treatment period, subjects are expected to administer one dose of study drug within 1 hour of experiencing moderate or severe migraine pain. During the DB2 treatment period, subjects are expected to take a single dose of study drug to treat another attack at any pain level.

The following will be presented for the SS, SS1, and SS2:

- The total number of study drug doses
- The number of days since randomization in DB1
- Number (%) of subjects who took at least one dose of study drug

The following will be presented for the SS and SS2:

- The number of days between the first dosing dates of DB1 and DB2

All study drug dosing information will be listed. For subjects who enter the DB2 period, the number of days between the first dosing dates of the DB1 and DB2 periods will also be listed.

### 9.2. RESCUE MEDICATIONS

Rescue medications are defined as medications taken to treat a migraine attack (in addition to the study drug) 2-24 hours after taking the study drug. Rescue medications taken during the study will either be reported in the eCRF based on entries in the subject eDiary, or will be reported outside of the eDiary. All rescue medications will be classified using the Anatomical Therapeutic Chemical (ATC) classification and preferred drug names from the World Health Organization Drug Dictionary (WHO-DD), version March 2016.

Summaries of rescue medications will be presented for the SS, SS1, and SS2 in tabular

form using the highest level ATC term as an upper classification and the preferred drug name as a lower classification level. All medications will be summarized by treatment group and overall and sorted by descending counts in the upper classification term and the lower classification term within the upper. For each subject, the medication will be counted only once within the upper classification level and only once within the lower classification level.

The number of rescue medication doses taken will be summarized by treatment group and overall for the SS, SS1, and SS2.

Separate listings will be provided for rescue medications taken during each DB treatment period.

### **9.3. ADVERSE EVENTS**

All AEs will be coded using the Medical Dictionary for Regulatory Activities (MedDRA; version 19.0 or higher). Migraine headaches will not be captured as AEs. Migraine headaches will be captured by the subject in the eDiary provided to them, and the information will be entered into the appropriate eCRF page.

All AEs will be listed by subject. The following listings of AEs will be provided:

- All AEs
- Study-drug related AEs
- Serious adverse events (SAEs)
- AEs leading to death
- Adverse events leading to study-drug termination

Only TEAEs will be included in summary tables. Summaries for AEs will be presented for the SS, SS1, and SS2. An overall summary table of TEAEs will be produced for the following categories:

- Any TEAE
- Study-drug related TEAEs
- Serious TEAEs
- TEAEs leading to study-drug termination
- TEAEs leading to death

All TEAEs will be classified by system organ class (SOC) and preferred term (PT). Frequency count and the number of unique subjects of a TEAE will be tabulated by treatment(s) received. For the number of unique subjects reporting, if a subject reported more than one AE that was coded to the same SOC or PT, the subject will be counted only once for that specific SOC or PT.

The following summaries of TEAEs will also be provided:

- TEAEs by SOC and PT
- Study-drug related TEAEs by SOC and PT
- Serious TEAEs by SOC and PT
- TEAEs by maximum severity (mild, moderate, severe or missing) by SOC and PT
- TEAEs by strongest causality relationship (not related, possibly related, probably related, definitely related or missing) by SOC and PT

For TEAEs presented by relationship to study treatment(s), the strongest relationship to study treatment(s) during the study will be presented for each subject if coded to the same SOC or PT. For TEAEs presented by severity, the worst severity during the study will be presented for each subject if coded to the same SOC or PT. TEAEs with missing causality will be counted as related. TEAEs with missing severity will be counted as severe. The same will be true in the individual summaries.

#### **9.4. LABORATORY EVALUATIONS**

Abnormal-clinically significant lab results for clinical laboratory categories including hematology, clinical chemistry, serology, TSH, urinalysis, as well as results for urine drug screens and serum and urine pregnancy tests will be recorded on the eCRF. Parameters will be standardized according to the International System of Units (SI) prior to summarization. Baseline and post-baseline assessments, as well as the change from baseline, will be summarized for hematology, clinical chemistry, and urinalysis using descriptive statistics. The overall clinical significance and shift from baseline to end of study assessments will be provided in a summary table for hematology, clinical chemistry, and urinalysis. Summaries for laboratory evaluations will be presented for the SS, SS1, and SS2. Separate listings will be produced for each laboratory test group (hematology, clinical chemistry, serology/TSH, urinalysis, urine drug screens, and serum and urine pregnancy tests).

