### **3.6. TREATMENT ASSIGNMENT & BLINDING**

The DFN-15-CD-006 study is a randomized, 2 DB treatment period, placebo-controlled study. Eligible subjects will be randomized in a 1:1 ratio in both DB periods to receive orally either DFN-15 or matching placebo, to be used in one migraine attack. The randomization schemes for both DB periods will be generated by the biostatistics group of [REDACTED]. The interactive web response system (IWRS) will assign the appropriate study kit to each subject for each DB treatment period. If a subject discontinues from the study after randomization, the subject identification (ID) number and randomization number will not be reused, and the subject will not be allowed to re-enter the study.

All randomization data will be kept strictly confidential and accessible only to authorized personnel until the time of unblinding after database lock at the end of the study. Blinding is critical to the integrity of this clinical study; however, in the event of a medical emergency for an individual subject, in which knowledge of the treatment assignment is critical to the subject's management, the blind for the subject may be broken by the Investigator (or designee) by contacting IWRS. Before unblinding, the Investigator (or designee) should have determined that the treatment information is necessary to decide the subject's immediate management, and must make every effort to contact the Medical Monitor prior to unblinding. In many cases, especially if the emergency is clearly not related to study treatment, the problem may be properly managed without unblinding by assuming that the subject is receiving active treatment. In cases of accidental unblinding or when the Medical Monitor cannot be contacted prior to unblinding, the Medical Monitor should be contacted as soon as possible after the breaking of the blind and every attempt to preserve the blind for all other study staff should be made.

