### **3.8. STUDY PROCEDURES AND FLOWCHART**

The duration of study participation will be up to approximately 13 weeks, including a screening period of approximately 3 weeks, 2 DB treatment periods with up to 4 weeks allowed to experience and treat a migraine attack in each, and 2 to 7 days for subjects to return to the site after treatment.

[Table 1](#) summarizes the planned study assessments.

[Table 2](#) summarizes the eDiary assessments.

Table 1 Schedule of Assessments

	V1	V2	V3	V4  /ET 
	Screening	Randomization	End of DB1 period Re-randomization	End of DB2 period (end of study) or ET
Assessment	Approximately 21 days 	Baseline-Day 0  Study drug dispensed should be used to treat a migraine attack as soon as (and no more than within 1 hour after) experiencing moderate or severe pain.  Treatment should be completed within 4 weeks from Baseline.	Visit is expected within 2-7 days of treating a migraine attack with study drug dispensed at V2.  Study drug dispensed at this visit should be used within 4 weeks to treat a migraine attack at any pain level.	Visit is expected within 2-7 days of treating a migraine attack with the study drug dispensed at V3.  Once randomized, the total duration of each subject's participation in the study would be up to 10 weeks from Baseline.
Informed consent	X			
Inclusion/Exclusion criteria	X	X	X	
Subject eDiary instructions and dispensation 	X	X	X	
Adverse events (AEs) review	X	X	X	X
Demographics	X			
Medical history and prior medications	X	X		
Migraine history (including MBS for the co primary analysis) and current treatment status	X			
Physical examination and suicidality check 	X	X	X	X
Height and weight	X			X 

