**Statistical Analysis Plan**

**[name], Ltd.**  
**Protocol #DFN-15-CD-006**

**Amendment V3.0**

 V4 will occur up to 10 weeks after baseline (V2).

 Subjects who do not complete both DB periods will complete an ET visit.

 Subjects may be randomized earlier during this period if they meet inclusion/exclusion criteria and headache assessment criteria. The screening period may also be extended based on Investigator judgment and in consultation with the Medical Monitor.

 Before eDiary dispensing, initial screening should determine to the extent possible that the subject may be eligible for the study and is able, willing, and understands after being instructed how to use the eDiary; eDiary will be dispensed once if the subject is randomized and used throughout the DB periods. At V2, randomized subjects will be re instructed and re trained on the eDiary usage to ensure real time entry of predose and postdose assessments and the level of migraine pain to treat (moderate or severe for first treatment and of any pain level for the second). Thereafter, randomized subjects will be re instructed on eDiary usage, and re trained on instructions as needed.

 Physical examination data will be recorded in the source at screening (V1). A complete physical examination will be performed, including examination of head, eyes, ears, nose, and throat [HEENT], heart, lungs, abdomen, skin, cervical and axillary lymph nodes, neurological, and musculoskeletal systems. At other visits, symptom driven limited physical examination will be performed. Any subsequent untoward change during the study will be recorded as an AE. Suicidality risk will be determined and recorded at screening (V1) and checked at all subsequent visits. Significant suicide risk, in the opinion of the Investigator, is exclusionary at V1 and V2. A randomized subject will be discontinued if a significant suicide risk is determined at subsequent visits. At any visit, subjects who are a suicide risk should be referred to a mental health specialist. The Medical Monitor should also be notified.

 Weight only.

 Serum pregnancy test will be performed at screening (V1) for all female subjects of childbearing potential.

 Urine pregnancy tests will be performed at all study visits after screening for all female subjects of childbearing potential.

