### 5.3. SAFETY SET

The Safety Set (SS) will include all subjects who took at least one dose of DB study drug during one or both treatment periods, and have it recorded in their eDiary. Subjects will be analyzed according to the treatment they receive. The Safety Set 1 (SS1) will include randomized subjects who took at least one dose of DB study drug during the DB1 treatment period. The Safety Set 2 (SS2) will include subjects who were re-randomized and took at least one dose of DB study drug during the DB2 treatment period. The SS, SS1, and SS2 will be used for all analyses of safety endpoints including summaries of TEAEs, ECGs, and clinical laboratory results.

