#### **9.6. TWELVE-LEAD ECG**

Twelve-lead ECGs will be performed at screening and at every study visit. The overall ECG interpretation and shift from baseline to end of study assessments, as well as the change from baseline, will be summarized for the SS, SS1, and SS2.

All ECG findings collected in the CRF will be listed.

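### The SS1 laboratory and ECG shift tables end after the re-randomized DB2 dose, which dilutes any DB1 effect that does not last until V4

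*SAP*

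**What the plan says.** For hematology, chemistry and urinalysis, SAP 9.4 states: "The overall clinical significance and shift from baseline to end of study assessments will be provided in a summary table". The same section adds: "Summaries for laboratory evaluations will be presented for the SS, SS1, and SS2". SAP 9.6 uses the same window for ECGs, again for SS, SS1 and SS2: "The overall ECG interpretation and shift from baseline to end of study assessments, as well as the change from baseline, will be summarized". Neither section gives SS1 an end point of its own.

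SAP Table 1 (section 3.8) heads the V4/ET column "End of DB2 period (end of study) or ET" and labels V3 as the end of DB1. A footnote to that table adds: "Subjects who do not complete both DB periods will complete an ET visit".

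SAP 5.3 defines the DB1 set: "The Safety Set 1 (SS1) will include randomized subjects who took at least one dose of DB study drug during the DB1 treatment period". Whether the subject went on to DB2 does not matter for membership. On allocation, SAP 3.6 states: "Eligible subjects will be randomized in a 1:1 ratio in both DB periods to receive orally either DFN-15 or matching placebo". No dependence of the DB2 assignment on the DB1 arm is described.

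**The concern.** A reader will take an SS1 shift table with DFN-15 and placebo columns as a comparison of the two DB1 arms. For a subject who was dosed again, the closing value comes after a second, independently allocated dose. About half of the continuing subjects in each DB1 column will have taken DFN-15 most recently, and about half placebo.

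V3 is the reading that belongs to DB1. Laboratory tests and an ECG are done then, 2 to 7 days after the DB1 dose and before any DB2 drug is taken. For continuing subjects the shift table as worded does not use it.

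The SAP separates the periods elsewhere. Section 6.2.5 closes the DB1 TEAE window at the DB2 dose if that comes before day 5, and section 6.2.1 resets baseline for each period. The shift end point is where that separation is missing.

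At stake is a falsely reassuring table. A small number of normal-to-abnormal moves caused by the DB1 dose could have resolved by V4, or could be mixed with moves caused by the DB2 dose in both columns.

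**Working it through.** The plan states no figure on this point, so there is nothing to reproduce. The check is arithmetic on exposure.

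**Inputs from the documents**
- Shift window: baseline to end of study, which is V4/ET (SAP 9.4, 9.6, Table 1).
- SS1: everyone dosed in DB1 (SAP 5.3). Columns are read as the DB1 treatment (SAP 5.3 and 6.1.1).
- DB2 allocation: 1:1 (SAP 3.6).
- V3 is 2 to 7 days after the DB1 dose (protocol 9.2.1.3). The DB2 dose is due within 4 weeks of V3 (SAP Table 1). V4 is 2 to 7 days after the DB2 dose (protocol 9.2.1.4).

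**Assumptions**
- c is the share of SS1 that takes a DB2 dose, equal in both DB1 arms. The documents do not give it, so a range is shown. The 15% dropout in the sample-size section is a different quantity and is not used as an estimate of c.
- DB2 allocation is independent of the DB1 arm.
- The effect does not persist from the DB1 dose to V4, and it is the same size after either dose.
- Subjects with no DB2 dose have a last reading that still reflects DB1.

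**Step 1: interval from DB1 dose to V4 in completers.** Shortest: 2 + 0 + 2 = 4 days. Longest: 7 + 28 + 7 = 42 days. V4 can therefore be far from the DB1 dose.

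**Step 2: share of each SS1 column whose last dose before V4/ET was DFN-15.**
- DB1 DFN-15 column: (1 - c) + 0.5c
- DB1 placebo column: 0.5c
- Difference: 1 - c

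| c | DFN-15 column | Placebo column | Difference |
|---|---|---|---|
| 70% | 65.0% | 35.0% | 30 points |
| 85% | 57.5% | 42.5% | 15 points |
| 90% | 55.0% | 45.0% | 10 points |
| 95% | 52.5% | 47.5% | 5 points |
| 100% | 50.0% | 50.0% | 0 |

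If the table closed at V3, or at ET for subjects with no DB2 dose, the shares would be 100% and 0%, a difference of 100 points.

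**Step 3: effect on a shift rate.** Suppose, for illustration only, a shift risk of 2% after placebo and 6% after DFN-15, with c = 85%.
- DFN-15 column: 2% + 4% × 0.575 = 4.3%
- Placebo column: 2% + 4% × 0.425 = 3.7%

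The 4-point difference becomes 0.6 points, which is 0.15 × 4.

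**Step 4: relaxing non-persistence.** If a fraction r of the DB1 effect is still present at V4, then on an additive scale the retained share is (1 - c) + c × r. At r = 0 this is 1 - c, and at r = 1 nothing is lost.

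**The case against.** The strongest reply is that DB1 laboratory and ECG effects are examined elsewhere, and this is largely correct. SAP 9.4 and 9.6 also summarize change from baseline for SS1. SAP 6.4 keeps nominal visits, and protocol 10.5.6 asks for summaries by treatment group and time point, so V3 is compared by DB1 arm. Protocol 9.2.2.7 has clinically significant laboratory abnormalities reported as AEs, and SAP 9.3 tabulates TEAEs for SS1. A reader might infer that the first-dose safety comparison is lost from the plan, but these provisions show that it is not.

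These routes do not repair the shift table itself. Summaries of change can hide a few subjects who move from normal to abnormal, which is what a shift table is meant to show. The DB1 TEAE window closes at day 5 at the latest, while V3 may fall on day 6 or 7.

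A second reply is that the wording is loose and that end of study means the last assessment of the relevant period. The period-specific sets and baselines make that plausible. The table shells are not among the documents, so a V3 cut there cannot be excluded. The SAP text, however, ties end of study to V4/ET and states no exception for SS1.

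A third reply is that c and non-persistence are assumed. That is so, and the percentages are scenarios rather than an estimate for this trial.

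**Conclusion.** The point holds as one of dilution. Under the SAP text, the SS1 shift tables for laboratory data and ECGs close after the DB2 dose for every subject who takes one. A DB1 effect that does not persist to V4 then appears at about (1 - c) of its true size: 30%, 15% and 10% at c = 70%, 85% and 90%. This rests on independent 1:1 re-randomization, equal c in both arms, no persistence to V4, and ET readings close enough to the DB1 dose to reflect it.

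It is tempting to conclude that the table cannot show a DB1 effect at all, or that any drug-related shift would appear equally in both columns. The documents do not support that. SS1 includes subjects who never take a DB2 dose, and their ET value carries the DB1 contrast. A shift that lasts to V4 also stays visible in its DB1 column. The contrast vanishes only if everyone in SS1 takes a DB2 dose and nothing persists.

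Severity is minor. One descriptive safety display is affected, no hypothesis test is attached to it, and no efficacy conclusion changes.

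**What to change.** In SAP 9.4 and 9.6, replace the single end-of-study end point with one for each set:

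- **SS1:** baseline before the DB1 dose to V3, or to ET for subjects who take no DB2 dose. State which reading counts when such a subject has both.
- **SS2:** the pre-DB2 baseline to V4/ET. SAP 6.2.1 already defines that baseline, so this only makes the rule explicit for the shift tables.
- **Pooled SS:** if an end-of-study shift is kept, form the columns by actual exposure history (DFN-15 only, placebo only, both).

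The cost is SAP wording and table programming. Laboratory tests and ECGs are already scheduled at V3, so no new data are needed. If the shells already close the SS1 shift at V3, only the SAP text has to be brought into line.
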